5.1 Randomization and Blinding

Eligible subjects will be centrally randomized to study intervention prior to entering the Treatment Period using a randomization and trial supply management (RTSM) system. Subjects will be randomized to study treatment in a 2:1 ratio to receive either tildacerfont (starting at 50 mg QD) or matching placebo, stratified by screening dehydroepiandrosterone sulfate (DHEAS: $\leq 1.2 \times \text{ULN}$; $> 1.2 \times \text{ULN}$). At Week 4, subjects receiving tildacerfont will escalate their dose to 100 mg QD. At Week 8, subjects receiving tildacerfont will escalate their dose to 200 mg QD.

Investigators, site personnel, subjects, and the Sponsor's study team will be blinded to study treatment assignment. To maintain the blind, all subjects will receive the same number of study drug tablets, with the appropriate number of tildacerfont and/or placebo tablets for the assigned study intervention.

5.2 Study Treatment

5.2.1 Study Drug Administration

Subjects randomized to the tildacerfont group will initiate treatment with 4 weeks of 50 mg QD, then proceed to 4 weeks at 100 mg QD, and complete the study with 4 weeks at 200 mg QD. All placebo subjects will remain on placebo over the full 12-week Treatment Period.

5.2.2 Assessments

Appendix A: [Table 6](#) and [Table 7](#) show the schedule of events for the study.

5.2.2.1 Efficacy Hormone Assessments

The primary and secondary efficacy assessments are serum DHEAS. Exploratory efficacy assessments include adrenocorticotropic hormone (ACTH), dehydroepiandrosterone (DHEA), testosterone (T), androstenedione (A4), 17-hydroxyprogesterone (17-OHP), 11-ketoandrostenedione (11OHA4), 11 β -hydroxytestosterone (11OHT), 11-ketoandrostenedione (11KA4), and 11-ketotestosterone (11KT) will be measured. Efficacy hormone assessments will be collected Day 1, Week 4, Week 8, and Week 12 as shown in [Table 7](#).

5.2.3 Safety Assessments

Safety will be assessed by repeated clinical evaluations including adverse events (AEs), serious AEs (SAEs), AEs leading to discontinuation/withdrawal, dose limiting toxicities (DLTs), AEs of special interest (AESIs), physical examination, vital signs, electrocardiograms (ECGs), clinical laboratory tests (serum chemistry, hematology, coagulation, lipid panel, estimated glomerular filtration rate (eGFR), thyroid panel, cortisol, and urinalysis), and psychiatric evaluations for suicide risk by Columbia–Suicide Severity Rating Scale (C-SSRS).

5.2.3.1 Adverse Events

Investigators will collect information related to AEs throughout this clinical trial. All AEs occurring in all subjects will be collected following signing of the first informed consent until approximately 30 days after the last study treatment (Follow-up Visit).

5.2.3.2 Physical Examinations

A full physical examination should include assessments of the cardiovascular, respiratory, GI, neurological, and musculoskeletal systems; head, eyes, ears, neck, and throat (HEENT); thyroid; skin; and extremities. The full physical examination may exclude rectal, genitourinary, and breast exams.

An abbreviated physical examination includes the following components: cardiovascular, respiratory, abdomen, musculoskeletal, HEENT, and skin.

A full physical examination will be performed during the Day 1 and Week 12 visits. Abbreviated physical examinations will be performed at Week 4 and Week 8.

5.2.3.3 Vital Signs

The following vital signs will be assessed: blood pressure (systolic and diastolic; mmHg); pulse rate (beats per minute); respiration rate (breaths per minute); body temperature (°C); and weight (kg). Vital signs will be obtained at Screening, Day 1, Week 4, Week 8, and Week 12.

5.2.3.4 Electrocardiograms

All 12-lead electrocardiogram (ECG) assessments will include: heart rate, QRS, QT, and QTc intervals using Fridericia's formula. ECGs will be performed at the following visits: Screening, Day 1, Week 4, Week 8, and Week 12 as shown in [Table 7](#).

Clinically significant adverse findings from the ECG will be recorded on the AE CRF.

5.2.3.5 Clinical Laboratory and Urinalysis

Clinical laboratory assessments include serum chemistry, hematology, coagulation, lipid panel, thyroid panel, cortisol, and urinalysis. eGFR will be calculated from blood creatinine measured as part of screening clinical chemistry. Clinical lab assessments will be performed at Screening, Day 1, Week 4, Week 8, and Week 12.

Clinically significant adverse findings from laboratory or urinalysis assessments will be recorded on the AE CRF.

5.2.3.6 Psychiatric Evaluations

The Columbia–Suicide Severity Rating Scale will be used during the study to monitor suicidal ideation and behavior. The Baseline/Screening Version of the C-SSRS, which assesses both lifetime history and history from the last 12 months, will be used at the Screening Visit to determine subject eligibility. The Since Last Visit Version of the C-SSRS will be used at all subsequent visits (Day 1, Week 4, Week 8, and Week 12) specified in [Table 7](#).

[figure not shown]
5.2.4 Pharmacokinetic Measurements

A plasma samples will be collected for measurement of tildacerfont concentration at each on-treatment clinic visit (Day 1, Week 4, Week 8, Week 12) as indicated in [Table 7](#).

Spruce Biosciences, Inc.

Study SPR001-210 SAP

Version 2.0, 17 May 2023

Figure 1 Schema of Study SPR001-210 Study Visits

Abbreviations: d = day; DHEAS = dehydroepiandrosterone sulfate

6 STUDY OBJECTIVES AND ENDPOINTS

This study will evaluate the potential of tildacerfont to reduce and control DHEAS (change from baseline in DHEAS; $\geq 30\%$ (as well as 25% and 20%) reduction from baseline in DHEAS; DHEAS \leq ULN) in adult subjects with PCOS who have elevated baseline androgens.

Exploratory endpoints further explore the effect of tildacerfont on biomarkers (ACTH, DHEA, T, A4, 17-OHP, 11OHA4, 11OHT, 11KA4, and 11KT).

Study SPR001-210 will characterize biomarker outcomes up to 12 weeks of double-blind treatment (see [Table 1](#) for a summary of study objectives).

Table 1 Study 210 Objectives and Endpoints

	Objective	Efficacy Variable	Section Number
1.	Primary Efficacy		
1.1.	To evaluate the effect of tildacerfont in reducing DHEAS in subjects with PCOS and elevated adrenal androgens	Change from baseline in DHEAS at 12 weeks, 8 weeks, and 4 weeks on treatment	13.1
2.	Secondary Efficacy		
2.1.	To evaluate the effect of tildacerfont in achieving target reductions in DHEAS in subjects with PCOS and elevated adrenal androgens	Proportion of subjects who achieve $\geq 30\%$ reduction from baseline in DHEAS at 12 weeks, 8 weeks, and 4 weeks on treatment [1]	13.2
2.2.		Proportion of subjects who achieve DHEAS \leq ULN at 12 weeks, 8 weeks, and 4 weeks on treatment [2]	
3.	Exploratory Efficacy		
3.1.	To evaluate the effect of tildacerfont in reducing key serum hormones and androgens in subjects with PCOS and elevated adrenal androgens	Change from baseline at Week 12, Week 8, and Week 4 in ACTH	13.3
3.2.		Change from baseline at Week 12, Week 8, and Week 4 in DHEA	
3.3.		Change from baseline at Week 12, Week 8, and Week 4 in T	
3.4.		Change from baseline at Week 12, Week 8, and Week 4 in A4	
3.5.		Change from baseline at Week 12, Week 8, and Week 4 in 17-OHP	
3.6.		Change from baseline at Week 12, Week 8, and Week 4 in 11OHA4	

Objective	Efficacy Variable	Section Number
3.7.	Change from baseline at Week 12, Week 8, and Week 4 in 11OHT	
3.8.		
3.9.		
4. Safety		
4.1. To evaluate the safety of tildacerfont in subjects with CAH	AEs (SAE, AEs leading to treatment discontinuation, DLTs, AESIs), physical examination, clinical laboratory assessments (serum chemistry, hematology, coagulation, lipid panel, thyroid panel, cortisol, and urinalysis)	14

[1] Similar endpoints added in the analyses section for 25% and 20% reduction from baseline

[2] For subjects who enter the study with DHEAS values higher than ULN

6.1 Efficacy Objectives and Endpoints

6.1.1 Primary Efficacy

The primary objective of the study is to evaluate the effect of tildacerfont in reducing DHEAS levels in subjects with PCOS and elevated baseline adrenal androgens over the 12 weeks of double-blind, placebo-controlled, dose escalating treatment. The primary efficacy endpoint is the change in DHEAS from baseline ([Section 9.3.7](#)) at 12 weeks, 8 weeks, and 4 weeks on treatment.

6.1.2 Secondary Efficacy

The secondary objective evaluates the effect of tildacerfont in achieving adequate control of DHEAS in adult subjects with PCOS and elevated baseline adrenal androgens over the 12 weeks of double-blind, placebo-controlled, dose escalating treatment. The secondary efficacy endpoints are the proportion of subjects with a $\geq 30\%$, 25% and 20% reduction from baseline at Week 12, Week 8, and Week 4; and the proportion of subjects with DHEAS \leq ULN ([Section 9.3.11](#)) at Week 12, Week 8, and Week 4.

6.1.3 Exploratory Efficacy

The exploratory objectives of the study are to assess the effect of tildacerfont on biomarker control (ACTH, DHEA, T, A4, 17-OHP, 11OHA4, 11OHT, 11KA4, and 11KT) over the 12 weeks of double-blind, placebo-controlled, dose escalating treatment.

6.2 Safety Objective

The safety objective of the study is to evaluate the safety of tildacerfont in subjects with PCOS and elevated baseline adrenal androgens using safety assessments described in [Section 5.2.3](#).

7 SAMPLE SIZE AND POWER

A sample size of $n = 33$ subjects with 2:1 randomization will provide at least 80% power to detect a difference of 164 $\mu\text{g}/\text{dL}$ in mean DHEAS between at least one dose of tildacerfont and placebo, assuming a standard deviation of 154 $\mu\text{g}/\text{dL}$ and a two-sided alpha of 0.05. Accounting for a 15% drop out rate, the projected final sample size is $N = 39$ ($n = 26$ for tildacerfont, $n = 13$ for placebo).

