8.1. Sample Size Determination

A sample size of 33 subjects with 2:1 randomization will provide at least 80% power to detect a difference of 164 mcg/dL in mean DHEAS between at least one dose of tildacerfont and placebo assuming a standard deviation of 154 mcg/dL and a two-sided alpha of 0.05. Accounting for a 15% drop out, the final sample size is N=39 (n=26 for tildacerfont group and n=13 for placebo).

Subjects will be randomized using the strata of screening DHEAS ($\leq 1.2 \times \text{ULN}$, $> 1.2 \times \text{ULN}$).

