5 STUDY DESIGN

This is a multi-center, randomized, placebo-controlled, dose escalation clinical study that will evaluate the preliminary safety and efficacy of up to 12 weeks of double-blinded treatment with tildacerfont (50 mg, 100 mg, and 200 mg once daily [QD]) in adult women subjects with PCOS who have elevated adrenal androgens at baseline. Up to approximately 40 adult subjects will be randomized into the study.

Subjects who meet all eligibility criteria at Screening will be randomized into the Treatment Period in a 2:1 ratio to receive either tildacerfont or matching placebo. Subjects randomized to the tildacerfont group will receive 3 escalating dose levels of tildacerfont with each dose level administered for 4 weeks. Subjects randomized to placebo will remain on placebo over the full 12-week Treatment Period. Upon completion of the Treatment Period, subjects will return to the clinic within 30 days following their last dose for a Follow-up visit.

Clinical visits during the Treatment Period and Follow-up Period will include safety, efficacy, and PK assessments. [Figure 1](#) depicts study visits from Screening Period to Follow-up Period.

The maximum duration of Study SPR001-210 per subject is expected to be up to 204 days (i.e., up to 30 days of optional DHEAS screening, a maximum of 30-day Screening Period, a 12-week Treatment Period, and a 30-day safety Follow-up Period). Subjects randomized to tildacerfont will receive up to 12 weeks of treatment with tildacerfont. Assessments and procedures for evaluation of safety, efficacy, and PK will be conducted per the protocol-specified schedule (see Appendix A: [Table 6](#) and [Table 7](#)).

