15 CHANGES RELATIVE TO THE PROTOCOL-SPECIFIED ANALYSIS

The study intended to enroll up to 40 subjects but was discontinued early on the basis of a business decision made by the sponsor. Due to the resulting small sample size, the exploratory efficacy analyses described in Protocol [Section 8.3.4](#) are replaced with summaries of descriptive statistics.

The MMRM analysis introduced in [Section 13.1](#) of this SAP is not mentioned in the protocol. However, to avoid protocol amendment, inclusion of this analysis in the SAP – well in advance of the database lock – is meant to serve the same intent.

The secondary endpoint of 30% reduction from baseline in DHEAS is mentioned in the protocol and sections [6](#), [6.1.2](#), [9.3.12](#) and [13.2](#) of this SAP. However, since some subjects have entered the study up to 25% lower than anticipated DHEAS into the study, it is necessary to assess respond at lower threshold of reduction at 25% and 20% in addition to originally planned 30% reduction.

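### SAP Section 7 still presents N = 39 and at least 80% power as current, although Section 15 of the same version reports an early stop with a small sample

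*SAP*

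**What the plan says.** Protocol Section 8.1 sets the design on these inputs: 33 subjects allocated 2:1, a DHEAS difference of 164 mcg/dL for at least one dose against placebo, SD 154 mcg/dL, and two-sided testing at 0.05. SAP Section 7 restates it: 33 "subjects with 2:1 randomization will provide at least 80% power to detect a difference of 164" (in µg/dL). It then allows for 15% dropout and projects a final 39 subjects, 26 on tildacerfont and 13 on placebo.

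SAP Section 5 is also written in the future tense: "Up to approximately 40 adult subjects will be randomized into the study". It mentions neither 33 subjects nor power.

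SAP Section 15 then reports: "The study intended to enroll up to 40 subjects but was discontinued early on the basis of a business decision made by the sponsor". It attributes the replacement of the exploratory efficacy analyses by descriptive summaries to the small sample that resulted. Section 10.8 also cites small sample size as the reason for summarising subgroups descriptively.

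Section 13.1.3.1 keeps the formal Week 12 comparison of tildacerfont with placebo, with significance declared at two-sided p < 0.05. Section 13.2.1.1 keeps the responder tests at the 0.05 level.

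**The concern.** The statements in Sections 7 and 15 are both current text of SAP v2.0, dated 17 May 2023. When that version was written, the sponsor knew that enrolment had ended short of plan, so a projected N of 39 was already out of date. The sponsor acts on the small sample for the exploratory endpoints, but the only power statement that a reader can attach to the retained primary test is the planning one.

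SAP Section 4 says that the plan supports topline results and an abbreviated study report, and that its analyses may go into regulatory submissions or manuscripts. If the Section 7 text is carried forward unchanged, a non-significant Week 12 result could be read as negative evidence from a trial with 80% power. The plan gives no size at which to judge that.

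**Working it through.** **Inputs.** Difference d = 164 µg/dL, SD = 154 µg/dL, 2:1 allocation, two-sided alpha 0.05, dropout 15% (Protocol 8.1, SAP 7). The documents do not say whether 154 is the SD of DHEAS values or of changes; it is used as given. The achieved N appears nowhere in the documents.

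**Step 1: reproduce the plan.** With n1 = 22 and n2 = 11:

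- SE = 154 × √(1/22 + 1/11) = 56.87
- d/SE = 164/56.87 = 2.884
- Normal approximation: power = Φ(2.884 − 1.960) = 82.2%
- Noncentral t, 31 df, noncentrality 2.884: power = 79.8%
- Dropout: 33/(1 − 0.15) = 38.8, rounded up to 39, which splits 26/13

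The stated figures reproduce. The 0.2-point gap under the t-test comes from the choice of approximation and is not an error.

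**Step 2: the same calculation at smaller sizes.** Each row keeps 2:1 and the same d and SD. Power is from the noncentral t with n1 + n2 − 2 df. Half-width = t(0.975, n1 + n2 − 2) × SE.

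| Subjects analysed (assumed) | Split | Power, t-test | Power, normal approx. | 95% CI half-width (µg/dL) |
|---|---|---|---|---|
| 33 (plan) | 22/11 | 79.8% | 82.2% | 116 |
| 30 | 20/10 | 75.6% | 78.5% | 122 |
| 27 | 18/9 | 70.8% | 74.2% | 129 |
| 24 | 16/8 | 65.2% | 69.1% | 138 |
| 21 | 14/7 | 58.8% | 63.3% | 149 |
| 18 | 12/6 | 51.7% | 56.7% | 163 |
| 15 | 10/5 | 43.7% | 49.4% | 182 |
| 12 | 8/4 | 35.0% | 41.3% | 210 |

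By the normal approximation, power first falls below 80% at 31 subjects (79.2%). By the t-test it is just below 80% at 33. The plan therefore had almost no reserve beyond its dropout allowance. At 18 subjects the half-width (163) is about as large as the whole planned difference (164).

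**Step 3: how far the table applies.** It follows the plan's own basis, an unadjusted comparison in µg/dL. The primary model in SAP 13.1.3.1 is an ANCOVA on log-transformed change, with log baseline DHEAS and age as covariates. If 154 is an unadjusted SD and the covariates correlate 0.5 with the outcome (both assumptions), the residual SD on the raw scale is 154 × √(1 − 0.25) = 133.4. Power is then about 86% at 30 subjects, 82% at 27, 77% at 24 and 63% at 18.

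**The case against.** The strongest reply is that Section 7 is a design statement. It is conditional on 33 subjects, calls 39 a projection, matches the protocol, and is arithmetically right. A SAP normally restates the design basis. The early stop is also disclosed: SAP Section 4 says that changes are described in Section 15, and Section 15 reports the stop plainly. Section 13.1.4.2 requires a 95% confidence interval with the p-value, so the precision actually achieved will be reported. Section 10.6 calls the study exploratory and asks for caution. Recomputing power after enrolment has ended alters no analysis.

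Most of this stands, and it limits the point to an out-of-date statement of size and power. It does not remove the point. Section 7 does not label its figures as superseded or refer to Section 15, and Section 15 does not say how small the sample is. The caution in Section 10.6 concerns multiplicity, not low power.

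A reader might infer more than the documents support:

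- **That Section 5 also claims 33 subjects or 80% power.** It gives only an upper bound of about 40.
- **That the sample size calculation is wrong.** It reproduces.
- **That testing at p < 0.05 presupposes 80% power.** The threshold governs type I error and implies nothing about power.
- **That the early stop is hidden.** Section 15 states it.

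**Conclusion.** The point holds as a stale statement of size and power. Section 7 offers N = 39 and at least 80% power for a study that the same document says stopped early with a small sample, and nothing gives the achieved N or the power of the retained Week 12 test.

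The loss cannot be fixed at one number. On the plan's inputs it runs from about 4 percentage points at 30 subjects (79.8% to 75.6%) to about 45 points at 12 (79.8% to 35.0%). This assumes that 2:1 allocation was kept and that the comparison is unadjusted on the raw scale. Covariate adjustment could recover part of it. It is tempting to say that the primary test has become a coin toss, but that describes only sizes near 18 in the unadjusted table, and the documents do not show that the study ended there. No estimand, model or test is put in doubt.

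**What to change.** In SAP Section 7:

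1. Label 33 subjects, N = 39 and 80% as the original design basis.
2. State the actual number randomised. The pooled total is available without unblinding.
3. Cross-refer to Section 15.
4. Give the power for 164 µg/dL and the expected 95% CI half-width at that number, noting that both are on the raw, unadjusted scale and so do not correspond exactly to the log-scale ANCOVA. The planned 33 is the number before the 15% dropout allowance is added, so say whether the restated figures use subjects randomised or subjects expected to have Week 12 data.

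In SAP Section 5, replace the future-tense enrolment sentence with the actual number, or mark it as the original intention.

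The cost is a few lines of text and one short calculation, with no change to any analysis. The only downside is a less favourable stated power.

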8 ANALYSIS SETS

8.1 Intent-To-Treat Analysis Set

The Intent-To-Treat (ITT) Analysis Set will include all randomized subjects. The ITT Analysis Set will be the basis for demographics and baseline characteristics.

8.2 Modified Intent-To-Treat Analysis Set

The following modified ITT (mITT) Analysis Sets will include all randomized subjects who receive at least 1 dose of study drug (tildacerfont or placebo), have a baseline DHEAS assessment, and have at least one post-baseline DHEAS assessment. The mITT Analysis Set will be the basis for efficacy analyses.

8.3 Safety Analysis Set

The Safety (SAF) Analysis Set is defined as all subjects who received at least one dose of study drug (tildacerfont or placebo) during the Treatment Period. The safety analysis set, which will be summarized based on the actual randomized treatment administered, will be used for evaluation of study drug exposure, concomitant medication, and safety.

9 GENERAL CONSIDERATIONS

Data summarization and presentation conventions are documented in a separate document for mock-shells.

9.1 Presentation of Summary Statistics

For most summary statistics, data will be analyzed and displayed in tabular format.

Unless otherwise specified, continuous efficacy hormones ([Section 5.2.2.1](#)) will be summarized using a 11-point descriptive statistics (i.e., n, mean, standard deviation [SD], median, 25% quartile [Q1], 75% quartile [Q3], minimum, maximum, geometric mean, geometric coefficient of variance [CV%], 95% confidence interval [CI] for geometric mean [including geometric mean ratio and its 95% CI]).

All other continuous variables will be summarized using an 8-point descriptive summary (n, mean, SD, median, Q1, Q3, minimum, and maximum) unless otherwise specified.

The same number of decimal places as in the observed value will be presented when reporting minimum and maximum; 1 additional decimal place than in the observed value will be presented when reporting mean, median, Q1, Q3, geometric mean, 95% CI; 2 additional decimal places than in the observed value will be presented when reporting SD. Geometric CV% will be reported to one decimal place.

All categorical/qualitative data will be presented using the frequency of events and percentages. All percentages will be presented to 1 decimal place, unless otherwise specified. Percentages equal to 100 will be presented as 100% and percentages will not be presented for zero frequencies, with the exception of binary variables. For summaries of AEs and concomitant medications (CMs), the percentages will be based on the number of subjects who received study drug.

All analyses and summaries will be produced using SAS® version 9.4.

9.2 Presentation of p-values

Results of statistical analyses will be reported using summary tables, listings, and figures (TLFs). The ICH of Technical Requirements for Pharmaceuticals for Human Use numbering convention will be used for all TLFs.

Unless otherwise noted, all statistical testing will be two-sided and will be performed at the 0.05 significance level. Tests will be declared statistically significant if the calculated p-value is < 0.05, unless otherwise specified. P-values will be reported with 4 significant digits except when reporting p-values less than 0.001, reported as < 0.001.

9.3 Definitions and Derived Variables

9.3.1 Screened and Enrolled Subjects

9.3.1.1 Screened Subjects

Subjects who signed an informed consent form are considered Screened Subjects

